After randomization and during the stimulation, all patients will be monitored closely by a physician-investigator. NIHSS will be obtained at the end of each 20-minute stimulation cycle and a visual inspection of the skin and rate degree of any potential erythema under the electrode will be performed. Then, a tolerability form will be completed based on validated cutaneous, neurological, and pain items of the PRO-CTAE (Patient-Reported Outcomes version of the Common Terminology Criteria for Adverse Events) (Figure 8).^{49,50}

After the stimulation, nursing neurologic assessments will be performed by Neurointensive Care Unit or Stroke Unit nurses with extensive experience in monitoring acute stroke patients. Specifically, patients will be monitored for any signs of neurological worsening and will be queried on development of new or worsening neurological symptoms including headache, dizziness, numbness, or weakness, etc. If any sign or symptom of neurological worsening is suspected, the patient will be immediately assessed by the on-call neurologist and an immediate brain imaging (CT or MRI) will be obtained. Neuro-checks will be performed at 1h and 2h after stimulation and then every 2 hours in patients requiring Neurointensive Care and every 4 hours in patients requiring Stroke Unit Care. Subsequent care will be continued in these settings, including medical management per national guidelines for acute ischemic stroke management issued by the American Stroke Association.⁵¹ Patients will not receive NSAIDs as concomitant therapy for the first 7 days after enrollment. All patients will undergo a multimodal MRI or CT including standard parenchymal images, non-invasive angiography, and perfusion studies and formal NIHSS assessment at 2-hour and 24-hour following the end of the stimulation tier as part of the study protocol.

D.6. Study Visits and Data Acquisition

D.6.1 Schedule of Events

	Baseline	End of each 20-min stimulation cycle			2-hr	24-hr	Day 4	Day 30	Day 90
		1	2	3					
Consent	✓								
History / Exam	✓								
Routine Labs	✓								
Vital Signs	✓	✓	✓	✓					
Patient tolerability form		✓	✓	✓					
Technician tolerability form/Skin Inspection*	✓	✓	✓	✓					
Multimodal MRI or CT	✓				✓	✓			
NIHSS	✓	✓	✓	✓	✓	✓			✓
Modified Rankin Scale (mRS)	✓						✓	✓	✓
Barthel Index (BI)									✓
EuroQol (EQ-5D)									✓
AMC Linear Disability Scale									✓
Interval serious adverse events		✓	✓	✓	✓	✓	✓	✓	✓

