Emergent multimodal MRI or CT is currently acquired as the routine initial imaging study in all acute stroke patients at UCLA without contraindications such as the presence of a pacemaker or metal implant. A 1.5 T or 3 T scanner equipped with echo-planar imaging capability is used for rapid acquisition of diffusion and perfusion scans. The standard clinical MRI protocol includes Gradient Recall- Echo (GRE), DWI, FLAIR (Fluid-Attenuated Recovery Image), PWI and MR angiography. The ADC (apparent -diffusion coefficient) values derived from DWI acquisition ($b=0$, 1000 s/mm^2 applied in each of three principal gradient directions) will be used to delineate the volume of ischemic core. The tissue with ADC values of $\leq 620 \mu\text{m}^2/\text{s}$ will be considered ischemic core, indicative of tissue with advanced, irreversible bioenergetic compromise. FLAIR delineates early parenchymal signal abnormality associated with ischemia and slow retrograde flow in leptomeningeal collaterals appearing as FLAIR vascular hyperintensity (FVH). The GRE sequence is used to evaluate the presence of intracranial hemorrhage and deoxygenated leptomeningeal collaterals appearing as GRE vascular hypointensity (GVH). PWI is acquired with sequential T2*-weighted (gradient echo) EPI time sequence scanning. Early in the time series, a bolus (0.1 mmol/kg) of MRI contrast material is rapidly infused (5 ml/sec through an 18 or larger gauge angiocatheter) using a power injector. The perfusion lesion volume (tissue at risk volume) will be the region with $\text{Tmax} \geq 6\text{sec}$ (Tmax = the time delay from the arrival of contrast to its peak concentration at the tissue vasculature).^{52,53} Intracranial CEMRA (Contrast-Enhanced MRA) will identify large and medium vessel occlusion.

In patients receiving CT, the standard clinical CT protocol includes non-contrast CT (NCCT), multiphase CT angiography, CT perfusion (CTP) processed through RAPID software. NCCT is used to rule out acute intracranial hemorrhage appearing as hyperdensity. The tissue with $\text{rCBF} < 30\%$ on CTP will be considered ischemic core and the perfusion lesion volume (tissue at risk volume) will be the region with $\text{Tmax} \geq 6\text{sec}$. CT angiography (CTA) will identify large and medium vessel occlusion.

- 2h and 24h Post-Stimulation

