Follow-up MR or CT imaging will be obtained 2h and 24h post-stimulation (supported by Radiology Dept. research funds). MRI Imaging sequences will include DWI/FLAIR/GRE/PWI/CEMRA and CT imaging sequences will consist of NCCT/CTA/CTP. RAPID image processing software will be applied to the above images to quantify, at the baseline, 2h, and 24h time-points: 1) Ischemic Core volume, 2) Perfusion lesion volume, and 3) Penumbra volume (perfusion volume - core volume). From these values, the following measures will be constructed: 1) Early penumbra preservation: Volume of baseline penumbra tissue not progressing to ischemic core at 2h; 2) Penumbral salvage: Volume of baseline penumbra tissue not progressing to ischemic core at 24h; 3) Early collateral flow enhancement: Perfusion lesion volume at baseline – Perfusion lesion volume at 2h; 4) Sustained collateral flow enhancement: Perfusion lesion volume at baseline – Perfusion lesion volume at 24h; 5) Early infarct growth: Ischemic core lesion volume at 2h – Ischemic core lesion volume at baseline; and 6) Final infarct growth: Ischemic core lesion volume at 24h – Ischemic core lesion volume at baseline. Additional location and extent of ischemic injury at baseline, 2h, and 24h will be rated using the MRI ASPECTS scoring system, with regions considered involved if diffusion restriction is present in more than 20% of the region or CT ASCPETS.^{54,55} In patients receiving MRI, location and extent of FVH and GVH will be rated using the FVH-modified ASPECTS and GVH modified ASPECTS scales.⁵⁶

D.6.10 Adverse Events

D.6.10.1 Serious Adverse Events (SAEs)

All serious adverse events occurring during the 90 days of study participation will be recorded. A serious adverse event is any adverse event that is fatal, is life-threatening, is permanently or substantially disabling, requires or prolongs hospitalization, or requires medical or surgical intervention to prevent one of the above outcomes.¹⁹

D.6.10.2 Symptomatic intracranial hemorrhage

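### MRI or CT is allowed at baseline, 2h and 24h with a different core definition on each and no same-modality rule, so four exploratory core-based imaging endpoints can mix true change with a change of definition

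*Combined protocol and SAP*

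**What the plan says.** **Baseline (D.6.9).** "Emergent multimodal MRI or CT is currently acquired as the routine initial imaging study in all acute stroke patients".

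**Follow-up.** The section on management during and after stimulation (the second one numbered D.4) says "All patients will undergo a multimodal MRI or CT including standard parenchymal images, non-invasive angiography, and perfusion studies", at 2h and 24h. D.6.9 repeats it: "Follow-up MR or CT imaging will be obtained 2h and 24h post-stimulation". The schedule in D.6.1 also lists MRI or CT at all three times.

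**Core on MRI (D.6.9).** ADC values are what "will be used to delineate the volume of ischemic core". Tissue at or below 620 µm²/s "will be considered ischemic core, indicative of tissue with advanced, irreversible bioenergetic compromise".

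**Core on CT (D.6.9).** Tissue with rCBF <30% "on CTP will be considered ischemic core and the perfusion lesion volume" is again the region with Tmax ≥6 sec.

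**Endpoints (D.6.9).** "Final infarct growth: Ischemic core lesion volume at 24h" minus the baseline core volume, with the 2h version built the same way. Penumbra is perfusion volume minus core volume. Preservation and salvage are the baseline penumbra that has not become core by 2h and 24h. Collateral enhancement is baseline minus follow-up perfusion lesion volume.

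**Specific Aim III.** It describes the salvage, collateral and growth endpoints on MRI alone.

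**Status.** E.3.5.1 treats the imaging endpoints as exploratory, with means and 95% confidence intervals by arm and by higher and lower tiers. D.6.10.2 says that the choice of next development step will draw on all outcome measures.

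**The concern.** ADC measures water diffusion and rCBF measures blood flow, so the two thresholds need not outline the same tissue in the same patient at the same moment. A patient imaged by CT at baseline and MRI at 24h, or the reverse, complies with the protocol. That patient's infarct growth is then one kind of core minus another. The same applies to penumbral preservation and salvage, where baseline penumbra depends on one core definition and progression to core is judged by the other.

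Nothing in the text available for review ties follow-up modality to baseline modality, records a switch, or says how a mixed pair is analyzed. With 6 to 12 sham patients a single such value has visible weight in an arm mean. These endpoints test nothing formally, but they are among the results that will inform whether and how to proceed.

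A related reporting gap concerns asymptomatic ICH. D.6.9 evaluates hemorrhage on GRE in MRI patients and on non-contrast CT in CT patients, while E.2.3.3 analyzes a single rate.

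**Working it through.** **1. Reproduce the plan's sample size (E.2.1).** Six tiers with 3 active and 1 sham per cohort, one or two cohorts per tier:
- 6 × (3 + 1) = 24, that is 18 active and 6 sham.
- 6 × 2 × (3 + 1) = 48, that is 36 active and 12 sham.

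Both match the stated 24 to 48.

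**2. Permitted sequences.** Two modalities at three times give 2³ = 8 patterns. Two keep one modality throughout and 6 are mixed. Baseline and follow-up differ in 4 of 8 patterns at 2h and in 4 of 8 at 24h. These are counts of what the text permits, not probabilities.

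**3. What a mixed pair measures.** With modality A at baseline and B at follow-up:

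observed growth = [core at follow-up by A − core at baseline by A] + [core at follow-up by B − core at follow-up by A]

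The first bracket is growth. The second is the definitional offset.

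**4. Endpoints reached.**

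| Endpoint | Uses core | Affected |
|---|---|---|
| Infarct growth, 2h and 24h | yes | yes (2) |
| Penumbral preservation/salvage, 2h and 24h | yes | yes (2) |
| Collateral enhancement, 2h and 24h | no; Tmax ≥6 sec on both modalities | not by this mismatch (2) |

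**5. How often (assumed).** If a proportion p of patients has a mixed pair, the chance of at least one in the sham arm is 1 − (1 − p)ⁿ.

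| p | n = 6 | n = 12 |
|---|---|---|
| 10% | 47% | 72% |
| 20% | 74% | 93% |
| 30% | 88% | 99% |

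**6. Shift in an arm mean from one switched patient (assumed offset).** Shift = offset / n.

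| Offset | 6 sham | 12 sham | 18 active |
|---|---|---|---|
| 5 mL | 0.8 mL | 0.4 mL | 0.3 mL |
| 10 mL | 1.7 mL | 0.8 mL | 0.6 mL |
| 20 mL | 3.3 mL | 1.7 mL | 1.1 mL |

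**7. Unequal switching (assumed).** Bias in the arm contrast = offset × difference in switching proportion, if all switches go the same way. It runs from 5 × 0.10 = 0.5 mL to 20 × 0.30 = 6 mL. It does not shrink as N grows.

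**8. Compare with sampling error (assumed SD 10 to 30 mL).** Half-width = t(0.975, N − 2) × SD × √(1/n sham + 1/n active):
- N = 24: 9.8 to 29.3 mL.
- N = 48: 6.7 to 20.1 mL.

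Every shift in steps 6 and 7 is below the matching half-width. An extreme case reaches it: three of six sham patients switched in the same direction, none in the active arm and a 20 mL offset give 3 × 20 / 6 = 10 mL, against 9.8 mL at the smallest assumed SD.

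**The case against.** **One modality per patient may be intended.** D.6.9 speaks of patients receiving CT and patients receiving MRI, and its examples of MRI contraindications (pacemaker, metal implant) would persist to 24h. That makes switching less likely, but the wording does not fix modality over time, so the gap stands.

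**The magnitude is assumed.** Neither the offset nor the number of switches is in the documents, and switches in opposite directions would partly cancel. This stands, and the figures are illustrative only.

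**Consequence is low.** The endpoints are descriptive. SICH escalation, tolerability, feasibility and sample size do not use core volumes. This stands and sets the severity.

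**Restricting the main analysis to same-modality pairs would select on a post-randomization variable.** This also stands, so that restriction belongs in a sensitivity analysis.

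**Hemorrhage detection is a between-patient matter.** Correct. It is a companion reporting item and exists without any switch.

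Three stronger readings may tempt a reader:
- *Staff who know the arm choose the scanner.* The text does not say who chooses or whether that person is blinded, and part of the document was not available to this review. Moreover, only the 2h and 24h choices follow randomization, because baseline imaging supplies eligibility.
- *Sicker patients will be moved to CT.* Nothing says so. The immediate CT or MRI for suspected worsening is separate from the scheduled scans.
- *All six imaging endpoints are affected.* The collateral endpoints share one Tmax threshold, so no definitional mismatch is shown for them.

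**Conclusion.** The gap is real but minor. As written, the plan permits an ADC core to be subtracted from an rCBF core, or the reverse, and calls the result infarct growth. The two penumbral preservation/salvage endpoints have the same weakness.

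Under an assumed offset of 5 to 20 mL, one switched sham patient moves the sham mean by 0.8 to 3.3 mL (6 sham) or 0.4 to 1.7 mL (12 sham). With assumed SDs of 10 to 30 mL this is within sampling error. It is not shown that a few switches would decide the sign of the contrast: reaching even the narrowest half-width takes the extreme case in step 8. The point merits action because imbalance in switching is a bias that the reported interval does not represent, and because a scan taken on the other modality cannot be replaced later. Separately, Specific Aim III and D.6.9 disagree on whether these endpoints are MRI only.

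**What to change.** - In the management section (second D.4) and D.6.9, state that scheduled 2h and 24h imaging uses the baseline modality where feasible and not contraindicated.
- Record the modality at each time point and the reason for any switch.
- Keep all patients in the main descriptive analysis. Report the four core-based endpoints by modality pair, and add a sensitivity analysis limited to same-modality pairs.
- Tabulate asymptomatic ICH by 24h modality.
- Reconcile Specific Aim III with the later sections that allow CT.

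**Cost.** Protocol wording, a case report form field and some constraint on scanner scheduling. The modality subgroups will be small. Patients with a CT baseline keep a flow-based core at follow-up, so matching makes their change score consistent but does not turn it into a diffusion measure. Sample size and the escalation rule do not change.

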We will implement a traditional 3+3 (rule-based, modified Fibonacci) dose escalation design, with 3:1 randomization to active treatment vs sham control. There will be 6 dose tiers, reflecting increasing intensity and duration of stimulation: Tier 1 – 1 mA, single 20 - min cycle; Tier 2– 2 mA, single 20 min cycle; Tier 3 – 1 mA, 2 cycles of 20 min/20 min off; Tier 4– 2 mA, 2 cycles of 20 min/20 min off; Tier 5 – 1 mA, 3 cycles of 20 min/20 min off; Tier 6 – 2 mA, 3 cycles of 20 min/20 min off (Figure 7). Patients in the sham stimulation arm at all the tiers will have the cap and electrodes in place, and switches moved but without any delivered electrical stimulation. While the highest dose tier in this study is expected to be fully safe, based on preclinical and clinical studies^{12,19}, since this is a first-in-human study in acute stroke, a formal escalation to higher dose tiers is prudent.

Figure 7. This figure shows the 6 escalating tiers. Blue represents 1 mA and purple shows 2 mA of tDCS. Symptomatic ICH (SICH) in none of the three patients in a tier will result in escalation. However, SICH in one patient, 3 more patients and 1 sham will be enrolled at the same tier.

D.4. Management during and post stimulation period

Figure7: Technician-filled tolerability form	Presence		Severity		Effect on the study treatment (Shortened the stim duration)		Duration/Frequency			Treatment			
	A	P	M	Mod	S	Y	N	< 50 % of stim period	≥50% of stim period	lasted after stim period (min)	None	Con	Med
Adverse Events													
Rash													
Skin dryness													
Hair loss													
Itching													
Hives													
Skin Sensitivity to light													
Skin soreness													
Skin redness													
Skin darkening													
Numbness													
Tingling													
Dizziness													
General Pain													
Headache													

*A=Absent, Con=Conservative therapy such as cold pack and lotion, M= Mild, Mod=Moderate, Med=Medication such as topical steroid, N= No, P= Present, R: Resolved, S: Severe, Stim= Stimulation, Y=Yes.

Figure 8. Shows the technician-filled tolerability form. The selected items are based on the most common reported adverse effects associated with tDCS.

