E.3.5. Exploratory Efficacy Endpoints Analysis (Specific Aim 3)

E.3.5.1. Exploratory Imaging Biomarker Efficacy Endpoints

This study is underpowered to definitively determine efficacy, so all imaging efficacy analyses will be purely exploratory and descriptive. Imaging biomarker efficacy endpoints will be characterized in the active and sham patients, and in higher and lower dose tiers, using means and 95% confidence intervals. The six imaging efficacy endpoints of greatest interest that will be explored are: early and late penumbral salvage, early and late collateral flow enhancement, and early and late infarct growth.

E.3.5.2. Exploratory Clinical Efficacy Endpoints

This study is underpowered to definitively determine efficacy, so all clinical efficacy analyses will be purely exploratory and descriptive. Four clinical outcome measures were selected based on their reliability, familiarity to the neurologic community, and adaptability for use in patients who have had a stroke. These endpoints are: the modified Rankin Scale (mRS), a rating of global disability; the Barthel Index (BI), a measure of instrumental activities of daily living; the National Institutes of Health Stroke Scale (NIHSS), a measure of neurologic deficit severity; and the EuroQol (EQ-5D), an assessment of health-related quality of life; and AMC Linear Disability Scale, a granular degree of disability.

Clinical efficacy endpoints will be characterized in the active and sham patients, and in higher and lower dose tiers. Early course clinical efficacy endpoints of greatest interest that will be explored are: **1)** Normalized change in neurologic deficit from baseline to 24h (normalized delta NIHSS – linear variable, analyzed with means and 95% CIs; and **2)** Degree of neurologic deficit at 24h (NIHSS – quasi-linear variable, analyzed with means and 95% CIs). Final outcome clinical efficacy endpoints of greatest interest that will be explored are: **1)** Degree of disability at 90 days, assessed across all 7 levels of the modified Rankin Scale – ordinal variable, analyzed with medians (IQRs) and means (95% CIs); **2)** Functional independence (mRS 0-2) at 90 days – binary variable, analyzed with rates and 95% CIs; **3)** Granular degree of disability at 90 days (AMC Linear Disability Scale) – linear variable, analyzed with means and 95% CIs; and **4)** Health-related quality of life (EQ-5D) – linear variable, analyzed with means and 95% CIs.

References:

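### The 2-hour scan is timed from the end of stimulation, so longer tiers have more elapsed time in the two early core-based measures when tiers of different duration are compared

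*Combined protocol and SAP*

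**What the plan says.** - **Scan timing.** D.4 (Management during and post stimulation period) sets multimodal imaging and "formal NIHSS assessment at 2-hour and 24-hour following the end of the stimulation tier as part of the study protocol". D.6.9 repeats the anchor: "Follow-up MR or CT imaging will be obtained 2h and 24h post-stimulation".
- **Tier length.** D.4 (Dose Tiers and Randomization) states: "There will be 6 dose tiers, reflecting increasing intensity and duration of stimulation". The shortest is "Tier 1 – 1 mA, single 20 - min cycle", the middle pair is of the form "Tier 3 – 1 mA, 2 cycles of 20 min/20 min off", and the longest is "Tier 6 – 2 mA, 3 cycles of 20 min/20 min off".
- **Measures.** D.6.9 defines each imaging measure from the baseline scan with no time term, for example "Early infarct growth: Ischemic core lesion volume at 2h – Ischemic core lesion volume at baseline". Early penumbra preservation is the volume of baseline penumbra that has not become core by the 2-hour scan.
- **Analysis.** E.3.5.1 says "Imaging biomarker efficacy endpoints will be characterized in the active and sham patients, and in higher and lower dose tiers". The planned summaries are means with 95% confidence intervals. Higher and lower are not defined. The section labels these analyses exploratory and descriptive.
- **What is absent.** The documents give no adjustment for elapsed time, no rate per hour, and no limit on the age of the baseline scan at the start of stimulation.

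**The concern.** Enrolled patients are ineligible for both intravenous thrombolysis and thrombectomy, and section B.1.2 itself describes expansion of the irreversibly damaged core. If the core is still growing between baseline and the early scan, a patient in a longer tier has had more time to lose penumbra by that scan. This would be so even if the current did nothing. The tier description could then hide a benefit of longer stimulation or resemble harm from it.

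This matters because the Impact section expects the trial to point to the most promising regimens for later trials, and D.6.10.2 says the decision on further development will draw on all outcome measures. A wide confidence interval does not tell the reader that its centre has been displaced.

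**Working it through.** The plan states no figure for the scan offset, so there is none to reproduce. The design figure used below is the sample size in E.2.1, which does reproduce: 6 × (3 + 1) = 24 and 6 × (6 + 2) = 48.

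**Step 1: start of stimulation to scan.** For c cycles, start to end of the last stimulation is 20c + 20(c − 1) minutes.

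| Tiers | Cycles | Start to end (min) | Start to early scan, +120 | Start to late scan, +1440 |
|---|---|---|---|---|
| 1, 2 | 1 | 20 | 140 | 1460 |
| 3, 4 | 2 | 60 | 180 | 1500 |
| 5, 6 | 3 | 100 | 220 | 1540 |

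The largest gap is 80 minutes. From start, the ratio is 220/140 = 1.57 for the early scan and 1540/1460 = 1.05 for the late scan. The wording leaves open whether a final off period counts. If it counts in every tier, the gap stays at 80 minutes. If it counts only in multi-cycle tiers, the gap is 240 − 140 = 100 minutes.

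**Step 2: baseline scan to early scan.** Growth is measured from the baseline scan, so the lead time L from that scan to the start of stimulation must be added. The documents do not give L; 30 to 180 minutes is assumed.

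- Tiers 5-6 v 1-2: (L + 220)/(L + 140). L = 30 gives 250/170 = 1.47; L = 60 gives 280/200 = 1.40; L = 120 gives 340/260 = 1.31; L = 180 gives 400/320 = 1.25.
- Tiers 4-6 v 1-3: mean tier lengths are (60 + 100 + 100)/3 = 86.7 and (20 + 20 + 60)/3 = 33.3 minutes, a gap of 53 minutes. The ratio is (L + 206.7)/(L + 153.3). L = 30 gives 236.7/183.3 = 1.29; L = 180 gives 386.7/333.3 = 1.16.
- A longer lead shrinks the effect: at L = 360 even the extreme contrast is 580/500 = 1.16.

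Under linear growth and no treatment effect, these ratios of time are also the ratios of apparent early growth.

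**Step 3: absolute size.** The documents give no growth rate or SD. At an assumed 1 to 10 mL/h, 53 minutes adds 0.9 to 8.9 mL and 80 minutes adds 1.3 to 13.3 mL. With 9 v 9 active patients and an assumed SD of 10 to 30 mL, the SE of a difference is SD × √(2/9) = 4.7 to 14.1 mL.

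**Step 4: comparisons that escape.**

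- Tiers 1 and 2, 3 and 4, and 5 and 6 have equal lengths, so 1 mA v 2 mA within a pair is unaffected.
- With 3:1 allocation in each tier, mean tier length is 3 × 360/18 = 60 minutes in active and 360/6 = 60 minutes in sham, if sham follows its tier's schedule. D.4 implies this without stating it outright.

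**The case against.** The strongest reply is that little hangs on these numbers, and most of it stands.

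- E.3.5.1 plans means and intervals only, with no test and no rule for ranking tiers. Escalation under E.2.3.1 rests on symptomatic hemorrhage and review of safety data. A reader might infer that the timing will lead the trial to choose short regimens, or that it distorts escalation. The documents support neither: no passage ranks tiers by early infarct growth, and the Impact section speaks first of feasibility, tolerability and safety.
- The 1.25 to 1.47 range is the extreme contrast. With higher and lower undefined, tiers 4-6 v 1-3 is an equally natural reading and gives 1.16 to 1.29. Over much of the assumed range in Step 3 the shift is below one standard error.
- A reader might extend the point to perfusion change. Nothing in the documents shows that the perfusion lesion grows steadily with time, so no direction of bias is established. Dividing by hours could create one: if two tiers had the same perfusion reduction, tiers 5-6 would appear 20% to 32% worse (1/1.25 = 0.80; 1/1.47 = 0.68).
- Variation between patients in the age of the baseline scan is not shown to differ by tier. It adds noise rather than a tier bias.

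What the reply does not remove is the direction. For the two early core-based measures the displacement runs against longer tiers, it is foreseeable, and nothing in the plan corrects it. Imprecision is no reason to leave in a bias that can be taken out cheaply.

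**Conclusion.** The point holds for early infarct growth and early penumbra preservation, compared across tiers of different duration. Its relative size is 1.25 to 1.47 (tiers 5-6 v 1-2) or 1.16 to 1.29 (tiers 4-6 v 1-3). These figures rest on linear growth, no treatment effect and an assumed lead time of 30 to 180 minutes; slower late growth or a longer lead makes them smaller. The size in mL cannot be fixed from the documents.

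The 24-hour measures shift by only about 5%. The point does not reach the equal-length current comparisons, active versus sham (on the condition in Step 4) or the safety rule. It is an inexpensive improvement to an exploratory analysis, not a flaw in the trial's main conclusions.

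**What to change.** Leave the scan schedule unchanged. Timing the early scan 2 hours from the start of stimulation would equalise growth time, but time since the last stimulation would then be 100, 60 or 20 minutes by tier, which exchanges one imbalance for another. Instead:

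1. Record the clock times of the baseline scan, stimulation start and each follow-up scan.
2. Report the baseline-to-follow-up scan interval by tier.
3. In E.3.5.1, for comparisons across tiers of different duration, present early infarct growth and early penumbral loss (baseline penumbra that has become core by the early scan) per hour from baseline scan to early scan, beside the raw difference.
4. Report perfusion change raw, with the interval, and do not convert it to a rate.

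Set this before tier results are seen, so that the scale is not chosen afterwards. Same-duration sham can be shown only as support: there are 2 sham patients per tier pair at a total of 24, and at most 4 at 48.

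The cost is a few lines of analysis text. Scan times should be in the image headers, and the feasibility endpoint in E.3.4 already needs the start time. The drawback is that a per-hour rate assumes roughly linear growth, which is why the raw value stays.
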